6.5 Follow-up Visits

Visits 8 (Follow-up, Week 6 after End of Treatment Visit)

Subjects will return 6 weeks after their treatment has ended to assess if any changes have occurred in pain free walking duration, maximal walking duration during the 6 minute walking test. Subjects will have a Walking Impairment Questionnaire (WIQ) and Quality of Life Questionnaire (PAD-QOL) administered. The presence or absence of adverse events following withdrawal of study drug will be assessed.

Schedule of Events

Schedule of Events								
	Visit 1 Screening	Visit 2 Baseline	Study Visits 3-7					Follow-up Visit 8
Time Point		Day 0	Week 2	Week 4	Week 8	Week 12	Week 12	Week 18
Time estimates	4 hours	4 hours	1 hour	1 hour	1 hour	4 hours	4 hours	45 min
Obtain Consent	x							
Ankle brachial Index	x					x		
Duplex ultrasound ¹	x							
Arterial elasticity	X					X		
Questionnaires	x					x		x
Memory test	X							
Height, weight, lean and fat mass	X					X		
Treadmill test	x					x		x
6 minute walk	x	x					x	x
MRI		x					x	
Blood draw for labs	X	x	x	x	x	x	x	
Urine test		x					x	
Blood pressure ²	x	x	x	x	x	x	x	x
Pregnancy test ³	x	x	X	X	X	X	X	X
Receive drug/placebo		x	x	x	x			
Review blood pressure records and diary			x	x	x	x		

1. Screening visit could be 5 hours long if duplex ultrasound is required, if not it will last 4 hours.
2. Visit should occur within 24 hours of last dose of drug.
3. Blood draw at screening and end of treatment visit 1 are following 10 hour fasting to assess serum: creatinine and K⁺, sodium, glucose, and serum insulin. Study visits at weeks 2, 4 and 6 are also fasting 10 hours prior to blood draw to assess: serum glucose, creatinine and potassium.
4. Duplex ultrasound will be perform only on those patients without a duplex ultrasound for the diagnosis of renal artery stenosis within the last year.
5. NIH toolbox for cognitive function.

6. The treadmill GXT test will be used to determine pain free walking distance, maximal walking distance.
7. Subjects will be instructed to measure and record their blood pressure at home, 3 times daily during the treatment period.
8. For women of childbearing potential.

7. Data Handling and Record Keeping

6.6 Confidentiality

Information about study subjects will be kept confidential and managed according to the requirements of the Health Insurance Portability and Accountability Act of 1996 (HIPAA). Those regulations require a signed subject authorization informing the subject of the following:

- What protected health information (PHI) will be collected from subjects in this study
- Who will have access to that information and why
- Who will use or disclose that information
- The rights of a research subject to revoke their authorization for use of their PHI.

In the event that a subject revokes authorization to collect or use PHI, the investigator, by regulation, retains the ability to use all information collected prior to the revocation of subject authorization. For subjects that have revoked authorization to collect or use PHI, attempts should be made to obtain permission to collect at least vital status (i.e. that the subject is alive) at the end of their scheduled study period.

6.7 Types of Data

Data for this study will include safety, laboratory and outcome measures.

6.8 Record Retention

Per University of Minnesota policy all documents concerning the use of human subjects in research will be maintained for 3 years from completion of IRB-related work and 6 years for HIPAA. No record will be destroyed without the written consent of the sponsor-investigator.

The sponsor-investigator will permit authorized representatives of the University of Minnesota and regulatory agencies to examine (and when required by applicable law, copy) clinical records for the purposes of clinical site monitoring, quality assurance reviews, audits, and evaluation of the study safety and progress.

6.9 Source Documents

A source document is defined as the location where study-related data are initially recorded. Source documents for this study will include hard copy paper and/or electronic forms, laboratory printouts, and medical records onto or into which data will first be recorded.

6.10 Protocol Deviations

A protocol deviation is any noncompliance with the clinical trial protocol. The noncompliance may be either on the part of the subject, the investigator, or the study site staff. As a result of deviations, corrective actions are to be developed by the site and implemented promptly.

When a deviation from the protocol is necessary for an individual subject, the Investigator must complete a description of the deviation from the protocol and justification on the Protocol Deviation Form.

7 Study Auditing, and Inspecting

7.1 Auditing and Inspecting

This study will be monitored according to FDA/GCP guidelines. The investigator will allocate adequate time for such monitoring activities. The Investigator will also ensure that the monitor or other compliance or quality assurance reviewer is given access to all the above noted study-related documents and study related facilities (e.g. pharmacy, diagnostic laboratory, etc. and has adequate space to conduct the monitoring visit.

8 Safety and Adverse Events

8.1 Adverse Event Definitions and Reporting Guidelines

9.1.1 Adverse Event

An adverse event (AE) is any symptom, sign, illness or experience that develops or worsens in severity during the course of the study. Intercurrent illnesses or injuries should be regarded as adverse events. Abnormal results of diagnostic procedures are considered to be adverse events if the abnormality:

- results in study withdrawal
- is associated with a serious adverse event
- is associated with clinical signs or symptoms
- leads to additional treatment or to further diagnostic tests
- is considered by the investigator to be of clinical significance

9.1.1.1 Serious Adverse Events (SAE)

A serious adverse event (SAE) is any adverse event that is:

- Fatal
- Life-threatening
- Requires or prolongs a hospital stay
- Results in persistent or significant disability or incapacity
- A congenital anomaly or birth defect

Important medical events are events that may not be immediately life-threatening, but are clearly of major clinical significance and may be SAEs. They may jeopardize the subject, and may require intervention to prevent one or the other serious outcomes noted above.

Hospitalization

Hospitalization shall include any initial admission (even if less than 24 hours) to a healthcare facility as a result of a precipitating clinical adverse event; to include transfer within the hospital to an intensive care unit. Hospitalization or prolongation of hospitalization in the absence of a precipitating, clinical adverse event (e.g., for a preexisting condition not associated with a new adverse event or with a worsening of the preexisting condition; admission for a protocol- specified procedure) is not, in itself, a serious adverse effect.

9.1.1.2 Expected Adverse Events (AE)

Expected adverse events are those that are known to be associated with or have the potential to arise as a consequence of participation in the study.

9.1.2 Unexpected Adverse Event

An adverse event or suspected adverse reaction is considered unexpected if it is not listed in the Protocol at the specificity or severity that has been observed.

Unanticipated Problems Involving Risk to Subjects or Others (UPIRTSO)

An adverse event that in the opinion of the Principal Investigator is unexpected and related to the investigational agent.

Assessment of Severity

Categories	Definition
Definitely related	This relationship suggests that a definite causal relationship exists between the administration of the investigational agent and the AE, and other conditions (concurrent illness, progression/expression of disease state, or concurrent medication reaction) do not appear to explain the event.
Probably related	This relationship suggests that a reasonable temporal sequence of the event with investigational agent administration exists and, based upon the known or previously reported adverse reactions, or judgment based on the investigator's clinical experience, the association of the event with the investigational agent seems likely.
Possibly related	This relationship suggests that treatment with the investigational agent may have caused or contributed to the AE (i.e., the event follows a reasonable temporal sequence from the time of investigational agent administration and/or follows a known response pattern to the investigational agent but could also have been produced by other factors.)
Not related	This relationship suggests that there is no association between the investigational agent and the reported event.

The sponsor-investigator will make an assessment of severity for each AE and SAE reported during the study. The assessment will be based on the sponsor-investigator's clinical judgment.

Assessment of Causality

The sponsor-investigator will estimate the relationship between the investigational agent and the occurrence of

each AE or SAE by using his best clinical judgment. Other elements, such as the history of the underlying disease, concomitant therapy, other risk factors, and the temporal relationship of the event to administration of the investigational agent, will be considered and investigated.

An SAE may be recorded when the sponsor-investigator has minimal information to include in the initial report. The sponsor-investigator may change his opinion of the causality in light of follow-up information, with subsequent amendment of the SAE report.

Recording of Adverse Events

At each contact with the subject, the investigator must seek information on adverse events by specific questioning and, as appropriate, by examination. Information on all adverse events should be recorded immediately in the source document, and also in the appropriate adverse event module of the case report form (CRF). All clearly related signs, symptoms, and abnormal diagnostic procedures results should be recorded in the source document, though should be grouped under one diagnosis. A adverse event monitoring form will be use to interview patients during the biweekly phone call to assess presence or absence of adverse events.

All adverse events occurring during the study period must be recorded. The clinical course of each event should be followed until resolution, stabilization, or until it has been determined that the study treatment or participation is not the cause. Serious adverse events will be collected for the six month period following study product administration. Serious adverse events that are still ongoing at the end of the study period must be followed up to determine the final outcome. Any serious adverse event that occurs after the study period and is considered to be possibly related to the study treatment or study participation should be recorded and reported immediately.

9.1.2.1 Data and Safety Monitoring Board (DSMB)

[figure not shown]
Before recruitment of participants, an independent DSMB will be formed in accord with guidelines published by the U.S. Department of Human Health Services⁶¹ and the National Heart Lung and Blood Institute⁶². This board will be composed by a physician expert in the management of patients with PAD, a biostatistician and at least two investigators with expertise in current clinical trials conduct and methodology. Board members will be independent from the study and at least one will not be affiliated with the University of Minnesota. None of them will have any financial, proprietary, professional, or other interests that may affect impartial, independent decision-making that constitute a potential conflict of interest. This board will be in charge of 1) periodically reviewing and evaluate the accumulated study data for participant safety, study conduct and progress, and, when appropriate, efficacy, and 2) make recommendations to the principal investigators (PIs) and the Internal Review Board concerning the continuation, modification, or termination of the trial. A DSMB will be selected and meet before the start of recruitment and will design a plan of action, frequency of meetings and elaborate detail safety guidelines for this study.

9 Data Analysis

9.1 Statistical Methods

General baseline characteristics will be described using mean and proportions. Smirnov-Kolmogorov tests will be used to test normality of distribution of variables. For variables that do not follow the normal distribution, log transformation will be performed. Linear simple and multiple regressions will be performed to assess

association between the effects of Entresto on metabolic and physiological changes with clinical functional variables. Differences between the placebo and the

Entresto group will be assessed using independent sample t-test and Chi-square for quantitative and categorical variables, respectively. Change following the 12 week clinical trial in metabolic and physiological parameters will be assessed using paired sample t-test. Repeated measures analysis of covariance will also be used to evaluate differences between groups as a function of time. A p value < 0.05 will be used to determine statistical significance. Effect size (EF) calculated as $EF = (\text{mean Entresto group} - \text{mean placebo}$

group)/SD (control group) will be used to assess the clinical significance of the effects of Entresto⁶³. The PI will be in charge of performing all statistical calculations using SAS v 9.3 by SAS Institute Inc., Cary, NC. [name] Jr. Professor at the School of Public Health a statistician with more the 800 publications will be a consultant in statistical analysis of the data.

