1.2 Study Aims/Objectives

Primary Objective:

1. To assess the effects of 12 weeks of Entresto on the functional clinical parameters maximal walking duration, pain free walking duration and 6 minute walk test of patients with PAD.

Secondary Objective:

1. To assess if changes in functional clinical parameters are related to improvements in microvascular and mitochondrial function and to assess the effects of increasing NP activity on arterial elasticity.
2. To assess the time required for functional improvements (6 minute walk test) to return to baseline

values following 12 weeks of Entresto.

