3.6.3 Rationale for measuring oxidative phosphorylation using MRS

Phosphocreatine resynthesis rates have been used as a surrogate measure of mitochondrial function⁴⁹ and has been studied non-invasively using MRS⁵⁰. MRS measured PCr resynthesis rate is independent of arterial occlusion⁵¹ and has been used to study the effects of exercise training and age on mitochondrial function^{47,52}. Furthermore, the rate of PCr resynthesis in patients with PAD is 2/3 lower than age matched non-PAD individuals, partially explaining their limitations with mobility^{51,53,54}. Therefore, measuring PCr resynthesis non-invasively is especially advantageous in patients with PAD in whom performing serial biopsies can cause wound healing complications. We expect that in patients receiving Entresto the rate of resynthesis of PCr will be increased and it will be associated with improvements in mobility.

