9.2 Power analysis

Sample size for a double blind randomized clinical trial was determined using SAS version 9.3 (SAS Institute Inc., Cary, NC, USA). Sample size is based on the mean (SD) values obtain in a clinical trial that measured the effects of carperitide on pain free walking distance in patients with PAD 5. The mean (SD) pre post change in pain free walking distance was of 278 (240) m. [We have estimated that for a power 0.85 we will need 15 subjects per group to reject the null hypothesis with Type I error probability of 0.05] (Figure 6).

10 Clinical Management

[name] Assistant Professor in the Department of Medicine Division of Kidney Diseases and Hypertension will be the study physician for clinical trial. This includes adjusting the dose of Entresto (based on information obtain from the Entresto information sheet, Novartis), development of safety procedures and treatment of medical complications. The main PI ([name] MD PhD) will be the person directly in charge of admittance of patients into the study, performing and supervising the diagnostic tests and the metabolic, physiological and clinical functional testing.

11 Risks/Benefits

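### Section 9.1 does not say whether the regressions linking mechanistic change to function pool the arms or adjust for arm; pooled without an arm term, they can show an association that exists within neither arm.

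*Combined protocol and SAP*

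**What the plan says.** Secondary objective 1 (section 1.2) has two parts. The first is "To assess if changes in functional clinical parameters are related to improvements in microvascular and mitochondrial function". The second is "to assess the effects of increasing NP activity on arterial elasticity".

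For the first part, section 9.1 offers one sentence. It begins "Linear simple and multiple regressions will be performed to assess" and goes on "association between the effects of Entresto on metabolic and physiological changes with clinical functional variables". It does not list the covariates of the multiple regressions, name the analysis population, or say whether the functional variables enter as changes. No other section specifies this model.

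Treatment group does appear elsewhere in section 9.1. For the placebo and Entresto comparison the text reads "Entresto group will be assessed using independent sample t-test and Chi-square for quantitative and categorical variables, respectively", and it adds "Repeated measures analysis of covariance will also be used to evaluate differences between groups as a function of time". Neither analysis is said to relate mechanistic change to functional change.

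Section 3.6.3 states the expected result: "in patients receiving Entresto the rate of resynthesis of PCr will be increased and it will be associated with improvements in mobility". The hypothesis in section 1.3 likewise predicts better vascular and mitochondrial function together with better clinical function.

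**The concern.** A simple regression has one predictor. If that predictor is a mechanistic change and the 30 patients are pooled, arm cannot be in the model. The protocol predicts that the drug shifts both the predictor and the outcome. Entresto patients would then tend to lie high on both axes and placebo patients low on both, and a line through the two clusters slopes upward. This happens even if, inside each arm, patients with more mechanistic change gain no more function than the others.

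At stake is the mechanistic claim. Section 1.1.5 presents these measurements as the biological basis for recommending Entresto in PAD. A pooled slope could be read as support for that mechanism when it only restates that both means moved.

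**Working it through.** **Inputs from the documents.** 30 patients in two balanced groups (section 2.1), so 15 per arm. Mean (SD) change 278 (240) m, power 0.85, alpha 0.05 (section 9.2). Significance level 0.05 (section 9.1). Sidedness is not stated; two-sided is assumed.

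**Input not in the documents.** The standardised effect on any MRS or fMRI measure. It is assumed and shown as a range.

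**Step 1: reproduce the plan's figure.** Section 9.2 states "The mean (SD) pre post change in pain free walking distance was of 278 (240) m". The standardised effect is 278/240 = 1.158. For a two-sample t-test with n = 15 per arm, the noncentrality is 1.158 × √(15/2) = 3.17 on 28 degrees of freedom, and power is 0.865. At n = 14 it is 0.839. So 15 is the smallest n per arm that reaches 0.85, which matches the plan. It also shows that 1.16 SD works as a between-arm difference in the plan's own sizing.

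**Step 2: correlation created by pooling.** Let dy and dm be the between-arm shifts in function and mechanism, in within-arm SD units, with equal arms and zero within-arm correlation. The between-arm covariance is dy·dm/4 and each variance is 1 + d²/4, so

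r = (dy·dm/4) / √[(1 + dy²/4)(1 + dm²/4)].

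- dy = dm = 1.158: 0.335/1.335 = 0.25.
- dy = dm = 0.8: 0.16/1.16 = 0.14.
- dy = dm = 0.5: 0.0625/1.0625 = 0.06.

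**Step 3: false-positive rate of the slope test.** Simulation with 40,000 trials per setting, 15 per arm, normal data, zero within-arm correlation, two-sided 0.05.

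| Shift in function (SD) | Assumed shift in mechanism (SD) | Induced r | Pooled, no arm term | With arm term |
|---|---|---|---|---|
| 1.16 | 0 | 0.00 | 5.0% | about 5% |
| 1.16 | 0.2 | 0.05 | 6.1% | about 5% |
| 1.16 | 0.5 | 0.12 | 9.7% | about 5% |
| 1.16 | 0.8 | 0.19 | 16.9% | about 5% |
| 1.16 | 1.16 | 0.25 | 28.1% | about 5% |
| 1.16 | 1.5 | 0.30 | 39.0% | about 5% |
| 0.8 | 0.8 | 0.14 | 11.6% | about 5% |
| 0.5 | 0.5 | 0.06 | 5.9% | about 5% |

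A separate run of the 0.8/0.8 setting gave 11.4%, so 11 to 12% is a fair reading of that row.

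**Step 4: power for a true within-arm correlation.** Same sample size and test.

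| Within-arm correlation | Both arms, arm term (N = 30) | Both arms, no arm term, no drug effect (N = 30) | Entresto arm only (n = 15) |
|---|---|---|---|
| 0.3 | 0.36 | 0.37 | 0.19 |
| 0.4 | 0.59 | 0.61 | 0.32 |
| 0.5 | 0.81 | 0.83 | 0.50 |

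The arm term costs 1 to 2 points of power. Restricting to the Entresto arm keeps the false-positive rate near 5% but loses 17 to 31 points against the arm-adjusted model.

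**The case against.** The strongest reply is that the plan is silent here, not shown to be wrong. Three stronger conclusions are tempting, and the documents do not support them.

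- **That the planned regressions omit arm.** Section 9.1 also plans multiple regressions with unlisted covariates, and arm could be one of them. The sentence speaks of the effects of Entresto, and section 3.6.3 words its expectation for patients receiving Entresto, so an analysis of the Entresto arm alone is a plausible reading. This bias does not arise there.
- **That secondary objective 1 as a whole cannot be answered.** Its arterial elasticity part is a between-arm question, which the t-test and the repeated measures analysis can address. The first part can be answered once arm is in the model.
- **That 28% is the plan's error rate.** It requires a mechanistic shift as large as the functional one, and the documents give no figure for that. The rate stays at 5% if the drug moves only one variable and is about 6% if both shifts are 0.5 SD. The 1.16 SD is itself a pre-post change from a carperitide trial. The carperitide study described in section 1.1.5 had no placebo group and measured pain-free walking in 4 patients, which is a weak basis for a between-arm shift.

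All of this stands as a limit on the claim. It does not remove the point. Simple regressions are explicitly planned. Pooled, they cannot hold arm; restricted to one arm, they give up much of the power. The arm-adjusted model in both arms is better under either reading, and leaving the choice open lets it be made after the data are seen.

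**Conclusion.** The concern holds as a gap in specification with a real consequence under one natural reading. If the simple regressions pool the arms, they are confounded by arm whenever the drug moves both variables, which is what the protocol predicts. At the plan's functional effect, the false-positive rate rises from nominal to about 28% as the assumed mechanistic shift goes from 0 to 1.16 SD. These figures rest on 15 completers per arm, normal data, equal within-arm SDs, zero within-arm correlation and a two-sided test. Only the first part of secondary objective 1 is affected.

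**What to change.** In section 9.1, replace the general sentence with a stated model for the first part of secondary objective 1: functional change regressed on mechanistic change, using patients from both arms, with randomised arm as a covariate. Baseline function may be added for precision; it is not needed to remove the bias. Report the arm-adjusted slope with its 95% CI as the result, and label any unadjusted correlation as descriptive.

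The cost is a short edit and one degree of freedom per covariate. Two limits should be stated with the result. At N = 30, power for a within-arm correlation of 0.3 is only 0.36, so a null slope is weak evidence of no link. And the adjusted slope removes confounding by arm but does not by itself establish that the mechanism mediates the drug's effect.

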1.1.5 Clinical trial with carperitide, what do we still need to learn?

The effects on pain free walking duration (PFWD) of 2 weeks of intravenous infusion of carperitide, a homolog of ANP, were tested in PAD patients with different degrees of severity⁸. That study showed a decrease in pain at rest, an increase in ankle/brachial blood pressure index and in PFWD with minimal side effects. However, the study only had 13 patients, PFWD was assessed in 4 patients and did not have a placebo group and the functional and structural changes in mitochondria and the microvasculature were not determined. Assessing those parameters would provide a sound biological basis for the effects of increasing the activity levels of NPs on the functional clinical limitations and for recommending Entresto for the treatment of PAD.

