2.1 Study Design

This is a double blind, randomized, controlled clinical trial with a goal of enrolling 30 subjects. Individuals who meet the eligibility criteria will be admitted into the study and will be randomly assigned to 12 weeks of Entresto or the placebo group. A variable block randomization design will be used to ensure a balance in sample size between the two groups²⁸. Each patient will be given a series of life style and health questionnaires, ankle brachial index will be measured and they will perform a graded exercise test to determine, pain free and maximal walking duration. In addition they will also perform the 6 minute walking test. They will also have a fMRI and MRS at pre and post 12 weeks of the clinical trial.

Following the 12 weeks of the treatment period, patients will be evaluated at weeks 4 and 8 to assess if any changes occurred in PFWD MWD and the 6 minute walking test, life style and health questionnaires and the presence or absence of adverse events following withdrawal of Entresto or placebo.

3 Outcome Measures

3.1 Ankle brachial index (ABI), exercise testing, questionnaires, anthropometric measurements and blood pressure monitoring

Patients will have their ABI determined following standard procedures described by the American Heart Association³⁴. If the patient's ABI meets the inclusion criteria, then an exercise testing procedure to determine, PFWD and MWDt will be performed. In addition, on that same day the Mini Mental State Examination (MMSE), the Walking Impairment Questionnaire (WIQ), the NIH toolbox assessment test for memory and cognitive function will perform, and Quality of Life Questionnaire (PAD-QOL)³⁵ will be given to each participant. Body height and weight will be measured using standard anthropometric procedures³⁶. Ambulatory blood pressure monitors using the Omron BP742N (©Omron Healthcare Inc. Lake Forest, IL) will be provided and each participant will measure and record their own arm blood pressure three times a day for the duration of the study immediately after waking up, at noon before lunch and in the night before going to bed.

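### For the walking outcomes, section 9.1 plans two between-group analyses and does not say which decides; name one baseline-adjusted week-12 comparison.

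*Combined protocol and SAP*

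**What the plan says.** The primary objective (section 1.2) covers three walking outcomes: maximal walking duration, pain free walking duration and the 6 minute walk. Section 9.1 is the whole analysis plan for them. It gives two between-group methods:

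- Differences between placebo and the "Entresto group will be assessed using independent sample t-test and Chi-square for quantitative and categorical variables, respectively".
- "Repeated measures analysis of covariance will also be used to evaluate differences between groups as a function of time".

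A third sentence concerns within-group change and is limited to the mechanistic measures: "Change following the 12 week clinical trial in metabolic and physiological parameters will be assessed using paired sample t-test".

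The significance threshold is p < 0.05 throughout. The methods are not ranked. The t-test is not tied to the week-12 value or to the change, and the ANCOVA has no stated covariate, visit list or contrast.

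Section 9.2 sizes the trial from a carperitide study: "The mean (SD) pre post change in pain free walking distance was of 278 (240) m", and concludes that "for a power 0.85 we will need 15 subjects per group" at a type I error of 0.05. It names no test.

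The visits that would enter a repeated measures model are not settled either. Section 2.1 says: "Following the 12 weeks of the treatment period, patients will be evaluated at weeks 4 and 8". Section 6.5 and the Schedule of Events have a single follow-up visit 6 weeks after treatment (week 18).

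**The concern.** With 30 patients and a stated efficacy objective, the test that decides should be fixed before the data are seen. Here at least two are open for each walking outcome, and each can be read in more than one way. The t-test can be run on the week-12 value or on the change. The repeated measures model can be judged on a group-by-time effect or on a group difference at one visit, over a set of visits on which the sections disagree.

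Two things are at stake. If the choice follows the data, the false-positive rate for a single outcome exceeds 5%. If the least suitable reading is used, much of the planned power can be lost. A more efficient comparison is available from data the trial already collects.

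**Working it through.** **Inputs.** Difference 278 m, SD of pre-post change 240 m and 15 per group come from section 9.2; p < 0.05 is from 9.1 and is taken as two-sided. The pre-post correlation r is not in the documents and is assumed at 0.3, 0.5, 0.7 and 0.9. Baseline and week-12 variances are assumed equal.

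**Step 1: the plan's own figure.** For a two-sample t-test on change, the noncentrality is 278 / (240 × √(2/15)) = 3.17 on 28 df, and power is 0.865. At 14 per group it is 0.839, so 15 is the smallest number that reaches 0.85. Other readings of the same inputs do not give 15: the two-sided normal approximation gives 14, a one-sided t-test 12, and a paired (one-sample) t-test 9. The sample size therefore reproduces as a two-sided t-test on change.

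**Step 2: the standard deviation under each analysis.**

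- Change: 240.
- Week-12 value: 240 / √(2(1 − r)).
- ANCOVA residual: 240 / √(2(1 − r)) × √(1 − r²) = 240 × √((1 + r)/2). Its variance is (1 + r)/2 of the change-score variance.

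**Step 3: power at 278 m, 15 per group** (28 df for the t-tests, 27 for ANCOVA).

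| r | SD, week-12 value | SD, ANCOVA | Power, week-12 t-test | Power, change t-test | Power, ANCOVA |
|---|---|---|---|---|---|
| 0.3 | 202.8 | 193.5 | 0.952 | 0.865 | 0.966 |
| 0.5 | 240.0 | 207.8 | 0.865 | 0.865 | 0.942 |
| 0.7 | 309.8 | 221.3 | 0.660 | 0.865 | 0.912 |
| 0.9 | 536.7 | 233.9 | 0.278 | 0.865 | 0.880 |

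The ANCOVA column is the formula value. When chance baseline imbalance is simulated it falls by about 0.01, to 0.960, 0.932, 0.902 and 0.869.

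**Step 4: a smaller effect.** The 278 m is a pre-post change used as a between-group difference. Section 1.1.5 describes a carperitide study in which "PFWD was assessed in 4 patients and did not have a placebo group"; I assume it is the same source. At half the effect (139 m, assumed), power over the same four values of r is 0.44 / 0.34 / 0.22 / 0.11 for the week-12 t-test, 0.34 for the change t-test, and 0.48 / 0.42 / 0.38 / 0.35 for ANCOVA. The ordering of ANCOVA over change is unchanged.

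**Step 5: false positives from the open t-test.** Simulating no drug effect with 15 per group (200,000 trials per value of r), and counting a success if either the week-12 or the change t-test has p < 0.05, gives 8.9%, 9.1%, 9.4% and 9.6% for r = 0.3, 0.5, 0.7 and 0.9. This is for one outcome.

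**The case against.** The best defence is that 9.1 has a natural default. The t-test is the listed group comparison, 9.2 points to change, and the repeated measures model could serve the secondary objective on return to baseline after stopping. On that view one clarifying line would do, and a change t-test is a valid choice. Much of this stands: fixing the change t-test would also remove the ambiguity. But 9.2 sizes the trial without specifying its analysis, and 9.1 gives the repeated measures model to group differences in general, not to the follow-up question.

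It is also fair that the spread for the week-12 t-test is driven by the assumed r. Holding the SD of change at 240 makes the week-12 SD run from 203 to 537 m, and no figure in the documents anchors it.

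Four stronger readings are tempting and are not supported:

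- *Paired t-tests are a third rival for the primary outcomes.* Section 9.1 limits them to metabolic and physiological parameters, which it treats separately from clinical functional variables. For those parameters the independent t-test also supplies a placebo comparison.
- *The follow-up conflict affects every measure.* The schedule has MRI, ABI and arterial elasticity at one baseline and one end-of-treatment visit. With two time points and no covariate acting on the time contrast, the group-by-time test is the change t-test.
- *Trying all the listed tests inflates the error to 10% or more.* Such a figure needs a week-12 baseline ANCOVA among the competitors, and 9.1 does not literally list one. The 9% above uses only the two readings of the t-test that is listed.
- *The repeated measures model has a known power deficit.* Any figure would need an assumed fraction of the effect remaining off drug, and the documents give none.

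**Conclusion.** The concern holds for the three walking outcomes. Section 9.1 leaves two between-group analyses unranked and incompletely specified, and the sample size fits only a test on change that 9.1 does not name. The size is about 9% false positives for one outcome if the reading of the t-test follows the data, and power anywhere from 0.95 to 0.28 if the week-12 value is tested, against 0.865 for change. These rest on normal data, equal variances, complete follow-up and r between 0.3 and 0.9.

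Baseline ANCOVA is the better single choice, but not by much on power. The gain over change is about 0.10 at r = 0.3 (0.966 against 0.865) and 0.015 at r = 0.9, or nearly nothing (0.869 against 0.865) once baseline imbalance is simulated. The stronger reason is a single placebo-controlled answer per outcome, fixed in advance. This should be corrected; it does not call the number of patients into question.

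**What to change.** State in section 9.1 that, for each continuous outcome, the deciding between-group analysis is ANCOVA of the week-12 value on treatment, with the same measure's baseline value as covariate, in all randomised patients with data. Then:

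- If the repeated measures model is kept, include the baseline covariate and make the week-12 group difference its deciding contrast. Report post-treatment visits separately, once section 2.1 (weeks 4 and 8) and section 6.5 (week 6) are reconciled.
- Name the visit that supplies the 6 minute walk baseline. The Schedule of Events marks the test at Visits 1 and 2; the section 6.1 text lists it only at Visit 1.
- For the metabolic and physiological measures, use the same ANCOVA from baseline to end of treatment and label the paired t-tests descriptive. Glucose, creatinine and potassium are also drawn at interim visits (section 6.2), so say which two draws are used.

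The cost is a few sentences and one degree of freedom (28 to 27), with no new data, visits or patients. This does not settle multiplicity across the three walking outcomes, which needs its own rule.
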